## 8. FINANCE AND SUPPLY OF EQUIPMENT

The research costs for this study and LB's doctoral program have been supported by the National Institute for Health Research (NIHR) Academy through the Doctoral Clinical and Practitioner Academic Fellowship award. The award provides £ 320,00 and covers all research costs, service user and public involvement (PPI), PhD fees, and LB's salary. The doctoral study commenced in October 2024 to October 2028.

The research team has no financial interests or commercial ties related to this study. The study aims to develop an intervention to reduce distress, enhance service users' understanding and increase future involvement through advance care planning. The resulting intervention will be made freely available upon the study's completion.

There is no conflicting interests.

The staff time spent delivering the intervention will be considered an excess treatment cost associated with the study, which will be calculated and reported in a SoECAT form. The WP3 intervention will be delivered by currently employed practitioners as part of their regular work schedule, requiring no additional staffing.

## 9. DATA MANAGEMENT

### 9.1 Confidentiality

The study is compliant with the requirements of the General Data Protection Regulation (2016/679) and the UK Data Protection Act (2018). All Investigators and study site staff will comply with the requirements of the General Data Protection Regulation (2016/679) with regards to the collection, storage, processing and disclosure of personal information, and will uphold the Act's core principles. UCL is the data controller; the UCL Data Protection Officer is [name] ([[contact]](mailto:[contact])). The data processors are UCL research team and NHS staff.

Personal Data will be collected directly from participants and no data from the medical record systems by the UCL research team.

The study will be collecting the following personal data:

#### All participants:

- Name
- Contact details for arranging interview/ focus group/ workshops or testing (email or telephone details).
- Contact (address or email if the participant requests research findings, dissemination events or further information on study).
- Demographic information (gender, age, ethnicity).

#### For service users participants:

- GP and care team details.

- Mental health history (self-reported diagnosis, duration of contact with mental health services).
- Experience of MHA assessments (number of assessments, outcomes such as detention or voluntary admission).

**For staff participants:**

- Professional role (e.g., Approved Mental Health Professional, Psychiatrist, Community Mental Health Nurse).
- Work setting (e.g., inpatient, community mental health, crisis services).

**Data Storage**

Depending on the data it will be stored differently and is summarised below.

a) Forms and data with **participant names and other identifiable details** will be stored electronically with UCL Data Safe Haven or paper consent in locked storage. Only research team members who need access and they will have contracts or honorary UCL contracts and be trained on data protection and Data Safe Haven.

For example, i) Participant name and ID list. All participants will have chosen a pseudonym name for the study and the ID will be this name and a number.

ii) Participant name and contact details for arranging participation in study. For staff information on team. For service users in WP1 and WP3, GP and care team details for informing them of participation in the study.

iii) Participant name and email/ postal address for sharing further information on study, dissemination events and report/ findings (if participant agrees on Consent Forms).

iv) Consent Forms – Paper stored in locked storage and will be scanned to Data Safe Haven, or an electronic recording will be stored similarly.

v) Recordings of interviews or focus groups prior to transcribing.

b) Forms with **Pseudo-anonymised** information will be stored in a separate folder (electronically on UCL Data Safe Haven or paper in locked storage). This data will be kept separate from personal identifiable data to further safeguard confidentiality.

For example, i) Case Report Form (see list of details on the form below)

ii) Demographics forms with Participant ID (age, ethnicity, gender, service users - mental health service information and staff – role and profession).

c) **Anonymised** research data will be stored on UCL One Drive and/ or UCL NVivo data analyst software, and all paper information will be scanned or photographed. This data will be shared with research team including members of the LEAP. Access to the folders on One Drive and NVivo will be limited to named people and not available to wider UCL staff. During the interview and focus group, researchers will refrain from using participants names. Transcripts will be checked for any identifiable information by lead researcher (e.g. removing names of any people, organisations or places from the text).

For example, i) Anonymised transcripts.

ii) Notes and data from workshops

iii) Reflective memos after interviews/ focus groups.

iv) Drafts of intervention.

Other data recording, NHS staff will add a note to medical records of service user participants in WP1 and WP3. NHS sites will manage any paper or electronic data in secure facilities as described in their Standard Operating procedures or policies.

If any paper documents with Personal Identifiable Details will be in a locked bag if being moved between buildings from interview or focus group setting to the secure storage at UCL.

### **Information on Case Report Forms**

The Case Report Forms (CRFs) will not bear the participant's name or other personal identifiable data. The forms will have the participant ID number. These CSF will include participant demographic and mental health diagnosis and MHA assessment or role details, work package, consent type, researcher observations from interviews, focus group or testing session, participant suggestion, any emotional responses, any adverse events and any post-session actions or support provided.

**Data custodian** is [name] (BLE).

### **Data transfer**

This will happen in two instances

- a) Between NHS sites and research team via secure email
- b) Interview and focus group recordings will be transferred to an approved UCL transcription provider.

**Data maintenance** responsibility is UCL research team.

### **Data storage timelines**

Forms with participant names and contact details for arranging data collection (interviews, focus groups, workshops and testing sessions) will be stored for i) deleted immediately if person decides not to participate in study, ii) at the end of recruitment stage of each work package, if not participating, iii) at end of study or iv) after findings and dissemination shared if participant agreed.

Research data will be stored for 10 years in line with UCL policy. This data will include consent forms/ recordings, transcripts and other research documents,

### **Breaches in confidentiality**

During the study, it is possible that a participant may disclose a serious risk of harm to themselves or to others. In these instances, we would seek participants' consent to share the necessary information with the relevant clinical team. If this consent was not given, the participant would be made aware of the need to breach confidentiality in such instances in the Participant Information Sheet. Depending on the circumstances and time permitting, the researchers will seek advice from more senior research staff like the supervisors ([name] (SJ) and [name] (BLE) who are qualified mental health practitioners). Where the need to breach confidentiality was confirmed, the researcher would then contact a care coordinator or other appropriate clinician involved in the participant's care. However, if the concerns were immediate, we would breach confidentiality immediately, and contact the relevant safeguarding advisors and others, such as emergency services, as appropriate. This would be judged on a case-by-case basis, and confidentiality would only be breached for serious disclosures where there is substantial concern about immediate risk to self or others

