## 9.5 Personal Data breaches

Personal data breaches will be immediately reported to the UCL Information Security Group (ISG) and the UCL Data Protection Officer [name] ([[contact]](mailto:[contact])), and to the Sponsor via the [UCL JRO research incident reporting form](#) (as per form and guidance: <https://www.ucl.ac.uk/legal-services/guidance/reporting-loss-personal-data>). The following information will be provided: full details as to the nature of the breach, an indication as to the volume of material involved, and the sensitivity of the breach (and any timeframes that apply). Sites will additionally follow their Trust incident reporting mechanisms and will document this within their Trial Master File and Investigator Site File.

The study has robust procedures in place to manage risks associated with participant disclosures of harm. If a participant discloses a serious risk of harm to themselves or others, the research team will follow an established distress protocol. Where possible, researchers will seek explicit consent before sharing concerns with a mental health professional. However, if a significant risk remains and the participant withdraws consent, confidentiality may need to be breached in line with safeguarding laws.

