## 11. ASSESSMENT AND MANAGEMENT OF RISK

The table below summarise the risks and mitigations for testing the intervention above standard care that are being performed in a table:

Intervention	Potential risk	Risk Management
Interview of service user participants WP1	There may be a small possibility that the service user participant will get upset or emotionally distressed whilst taking part in the interviews and testing of intervention.	
What the study involves will be clearly explained to participants in the study information sheet and by researchers, and written informed consent will be received before participants join the study.
 
The interview topic guides will be developed with the study Lived Experience Advisory Panel (LEAP) that will consist of people with lived experience of MHA assessment.
 
If participants become distressed the study researcher will use their skills to make sure the participant feels as safe as possible. The lead researcher LB is an experienced mental health worker and has expertise in dealing with distress. The researchers will use guidance from sensitive subject research. This will include monitoring the participants' mental state, offering breaks, offering the opportunity to talk through their difficulties (if they want to), providing a safe and containing environment to conduct the research and ensuring a person-centred stance is taken. A distress protocol will be developed with the LEAP group to guide if a participant becomes upset.
 
A debriefing time will be offered after to discuss any emotions and questions raised in the interview and this time was viewed as valuable in a previous study.
 
Service user participants will be given a sheet with local and national support services for mental health (see Support Resources Sheet) for them to use after the interview if needed. We will also provide information on MHA assessments which the LEAP will develop.
 
For WP1, the participants will be asked to provide details of a support person- mental health worker, friend or family who they can talk to after if needed. Contact details will be requested at beginning of interview.
 
In the unlikely event that the participant becomes distressed, and it is not manageable by the researcher, will also contact their support person if there is concern that they are at a risk to themselves, or self-harming intent/suicide is disclosed. Each participant will be given a list of contacts if feeling any distress following the interview

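### Protocol 9.1 ends by limiting any breach of confidentiality to immediate risk, which read literally closes its own route for telling a clinician about a serious but non-immediate risk

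*Protocol*

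**What the plan says.** Section 9.1 of the protocol, under Breaches in confidentiality, starts from the premise that "it is possible that a participant may disclose a serious risk of harm to themselves or to others". Consent to share with the clinical team is sought first. If it is not given, the paragraph still foresees a need to breach in these instances, and names the participant information sheet as the place where participants are told so.

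Two routes follow. In the first, "Depending on the circumstances and time permitting, the researchers will seek advice from more senior research staff", and then "Where the need to breach confidentiality was confirmed, the researcher would then contact a care coordinator or other appropriate clinician". The second is introduced as a contrast: "if the concerns were immediate, we would breach confidentiality immediately", with safeguarding advisors and, where appropriate, emergency services contacted.

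The paragraph closes by saying that the matter is judged case by case and that "confidentiality would only be breached for serious disclosures where there is substantial concern about immediate risk to self or others".

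Section 9.5 (Personal Data breaches) returns to the subject. It says "If a participant discloses a serious risk of harm to themselves or others, the research team will follow an established distress protocol", and that "if a significant risk remains and the participant withdraws consent, confidentiality may need to be breached".

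**The concern.** The last sentence of 9.1 is worded as a limit on all breaches, and the limit is immediacy. The sentences before it provide for a breach where the risk is serious and there is time to take advice. Both cannot govern the same disclosure.

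Take a participant who tells the researcher of serious suicidal intent that is not immediate and refuses to have it shared. The middle of the paragraph lets the researcher inform a care coordinator once the need is confirmed. The last sentence, followed literally, forbids it.

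The research team may be the only people who hear this. Section 6.2 has WP1 service-user interviews run by the lead researcher, joined by a lived-experience panel member if the participant agrees. Section 7.1.1 has WP3 service users interviewed apart from their clinician.

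The information sheet also needs a single rule. If it promised a breach only for immediate risk, a clinician contact under the first route would go beyond what the participant was told. If it said serious risk, it would disagree with the last sentence of 9.1.

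**Working it through.** No arithmetic applies. The protocol states no figure on this point, and Section 10 records that there are no statistical considerations. The check sets the sentences side by side and asks what each allows when consent is refused.

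| Text | Condition for a breach | Immediacy required? |
|---|---|---|
| 9.1, opening sentences | Serious risk of harm, consent not given | No |
| 9.1, first route | Need confirmed, after senior advice if time permits; clinician contacted | No |
| 9.1, second route | Concern is immediate; act at once | Yes, for this route only |
| 9.1, last sentence | Serious disclosure and substantial concern about immediate risk; worded as the only case | Yes, for every breach |
| 9.5 | Significant risk remains, consent withdrawn; breach may be needed | No |

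Apply these to the two possible cases.

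1. Serious and immediate, consent refused. The second route says act at once. The last sentence allows it. There is no conflict.
2. Serious and not immediate, consent refused. The first route says take advice and, if the need is confirmed, contact a clinician. The last sentence does not allow it. Nothing in 9.5 rules it out.

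The conflict is confined to case 2, but case 2 is what the first route is for. The protocol does not use the term non-immediate. That reading comes from the time-permitting condition on the first route and from the contrast that introduces the second. Since an immediate concern is handled at once under the second route, adding immediacy as a condition for any breach leaves the first route with little or nothing to apply to.

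The closing sentence does keep the word serious, so it does not swap one measure of severity for another. What it adds is a condition on timing, and that addition causes the conflict.

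**The case against.** The strongest reply is that the closing sentence may qualify only the route just before it. The case-by-case remark follows directly on the sentence about immediate concerns and emergency services, and the paragraph's other operative sentences all point to breaching for serious risk. On that view this is one loosely drafted clause. The reply stands as an account of what was probably meant, and 9.5, with no immediacy condition, supports it. It does not remove the conflict, because the clause limits all breaches and nothing in it confines the limit to one route.

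A second reply is that safeguards exist. Section 5.4 has the care team and GP informed of participation. 9.1 names clinically qualified supervisors. Section 11 has an experienced lead researcher, provides for contacting the participant's support person, makes a care-team participant responsible for ongoing support in WP3, and has participants judged high risk seen where clinical staff are present. These make silence less likely. They do not say which sentence governs. The support-person step is also tied to distress the researcher cannot manage, and that person may be a friend or relative.

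A reader might infer more than the documents support, in three ways.

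- That 9.1 and 9.5 set three rival thresholds: serious, immediate and significant. They do not. Serious describes severity and immediate describes timing. Significant in 9.5 is ordinary variation, referring back to the serious risk named just before.
- That the protocol contradicts itself on whether a distress protocol exists, since 9.5 calls it established and Section 11 says "A distress protocol will be developed with the LEAP group to guide if a participant becomes upset". A document developed before interviews begin can be established when it is needed.
- That the problem is confined to service users. 9.1 speaks of any participant.

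**Conclusion.** The concern holds: the last sentence of 9.1 is wrong as written. Followed literally, it bars telling a clinician about a serious but non-immediate risk when consent is refused, which the same paragraph provides for and 9.5 does not rule out.

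Its extent is one sentence. It concerns safeguarding and has no effect on the objectives, sample or analysis. The protocol gives no rate for such disclosures, so no number of affected participants can be stated.

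The conclusion rests on reading the first route in 9.1 as covering risks that are serious but not immediate, which is the natural reading of the contrast the paragraph draws. It does not rest on the content of the information sheet or the distress protocol, which are not at hand, and it does not imply that researchers would in practice stay silent. If the sponsor did intend to limit breaches to immediate risk, the text still needs changing, but the other way: the advice-then-clinician route and 9.5 would have to be narrowed.

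**What to change.** Replace the closing sentence of 9.1 with wording that uses the paragraph's own threshold and lets immediacy decide only the speed of action, for example:

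> This would be judged case by case, and confidentiality would only be breached where there is substantial concern about a serious risk of harm to self or others; where the concern is immediate, this would be done without first seeking advice.

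Use the same threshold in the participant information sheet and the distress protocol before the first WP1 interview.

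As optional tidying, 9.5 could use the same risk term and cover consent that is refused as well as consent that is withdrawn. Section 11 needs no change.

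The cost is one reworded sentence in a protocol marked DRAFT 0.1, with matching wording in two supporting documents. No staff, visits or procedures are added.

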## 9.2 Data collection tools and source document identification

Data will be collected from participants by the research team and will be recorded specific case report forms (CRFs) or data collection tools such as electronic CRFs.

Where participant data is collected remotely through videocalls, we will leave a file note on the CRF documenting where (on the UCL Data Safe Haven) the audio-recorded data are stored. Similarly, any paper copies of forms (e.g. consent and demographic forms) location will also be recorded on CRF.

In this study, there is little source data and documents like the demographic information will be transcribed onto the CSF.

A source document list will be implemented prior to the start of the trial to identify:

- which data is to be recorded directly onto the CRF.
- which data is recorded firstly into source documents, such as medical notes, and then transcribed into the CRF; and
- which data is not to be recorded in the CRF but only recorded in source documents, e.g. participant questionnaires.

It is the responsibility of the investigator to ensure the accuracy of all data entered in the CRFs. After the delegation log will identify all those personnel with responsibilities for data collection and handling, including those who have access to the trial database.

For this study the data contained in CRF will be only taken from the participants and probably include the following:

- Demographic information and diagnosis
- Basic information about experience of MHA assessments, outcomes and other mental health history
- Roles and profession
- Type of consent given either on paper or an audio file for online.
- Who interviewed or which focus group attended (WP1)/ Workshop attended (WP2)/ Test session (WP3) with whom
- If any distress/ emotional response experienced in the interview
- Any adverse events
- Any details of the support plan agreed by the research team member and the participant.

**Transcripts of Interviews and Focus Groups (WP1 and WP2)** After the interviews and focus group data are transcribed, then the lead researcher LB will fully anonymise them through removing any direct or indirect personal identifiable details, for example, mention of named hospital or teams. Fully anonymised versions of the transcripts will be analysed using NVivo software and saved on UCL online drives with access limited to the research team, including Lived Experience Researchers (LEAP members) and the supervisory team.

## 9.3 Completing Case Report Forms

For this study, the CRF will be completed by the UCL research team and will be stored immediately on UCL Data Safe Haven electronically.

## 9.4 Data Handling

In the study, data will be collected from service users in accordance with the service user consent form, participant information sheet and sections [9.1] of this protocol.

The data will be collected by the UCL research team and NHS staff and UCL will act as data controller will act as the data controller of such data for the study.

[name], Division of Psychiatry, [name] will process, store and dispose of data in accordance with all applicable legal and regulatory requirements, including the Data Protection Act 2018 and any amendments thereto. Data which either personal data or pseudonymised will be stored centrally electronically on Data Safe Haven or in locked storage at UCL.

The data will not be transferred to any party not identified in this protocol and are not to be processed and/or transferred other than in accordance with the patients' consent.

Direct access to the data will be granted to authorised representatives from the Sponsor, host institution and the regulatory authorities to permit study-related monitoring, audits and inspections, in line with participant consent.

